Single agent topotecan or CAV (cyclophosphamide, doxorubicin and vincristine) are appropriate treatment regimens for patients with sensitive relapse. A randomized trial comparing topotecan to CAV showed a response rate of 24% for topotecan and 18% for CAV, which was not statistically significant, with median survival of 6 months for both. In this study, sensitive disease was defined as relapse more than 60 days (or 2 months) after the completion of first line chemotherapy. This study led to the U.S. Food and Drug Administration’s approval of intravenous topotecan with an indication for sensitive relapsed SCLC (> 60 days from completion of first line treatment).

In three single arm phase II studies, topotecan was studied in patients with recurrent or progressive SCLC after treatment with first line chemotherapy. The three studies stratified patients for sensitive disease (response to initial therapy for  $\geq$  90 days) or refractory disease (no response to initial therapy, or progression within 90 days after completing treatment) and included patients with stable brain metastases. The European Organization for Research and Treatment of Cancer study reported a 21.7% overall response rate (37.8% among sensitive patients, 6.4% among refractory patients) and a 33-week median duration of response. Depierre et al. showed a 14% response rate (median survival, 25.7 weeks) in sensitive patients and a 2% response

rate (median survival, 16.3 weeks) in refractory patients. In the third study, the response rates were similar - 19% (median survival, 26.6 weeks) and 3% (median survival, 20.4 weeks) for patients with sensitive and refractory disease, respectively. A pooled analysis of the sensitive patients treated with second-line topotecan in these three SCLC studies reported an 18% response rate.

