#### **5.1.2. Secondary**

[figure not shown]
The objective response rate (ORR) will be determined in each arm of the study by RECIST 1.1. Notably, topotecan leads to a differential response in SCLC patients with sensitive vs refractory disease, which we do not anticipate in those receiving pembrolizumab. With the cross-over design, we will be able to determine the ORR for pembrolizumab in the second- and third-line setting. Overall survival of patients in each arm of the study will be analyzed. The treatment-related toxicity of pembrolizumab and topotecan will be summarized by toxicity type and grade for each treatment arm.

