-  Baseline tumor imaging will include the following: CT chest and abdomen with contrast OR CT chest without contrast and MRI abdomen with/without gadolinium and imaging of other known sites of disease; and brain imaging with MRI with/without contrast (or CT with contrast if the patient cannot tolerate an MRI). Imaging of the pelvis should be performed as clinically indicated or if there is known metastases in the pelvis. The initial tumor imaging will be performed within 14 days prior to the first dose of study treatment. Scans performed as part of routine clinical management are acceptable for use as the screening scan if they are of diagnostic quality and performed within 14 days prior to the first dose of study treatment. On-study imaging will be performed every 6 weeks ( $42 \pm 7$  days) after the first dose of study treatment or more frequently if clinically indicated. **The timing for imaging studies should follow calendar days and should not be adjusted for delays in cycle starts or extension of topotecan or pembrolizumab cycle frequencies.** The same imaging technique should be used in a patient throughout the study. Local reading (investigator assessment with site radiology reading) will be used to determine eligibility and for patient management.
-  After first documentation of progression (if the patient is clinically stable) or response per RECIST 1.1 repeat imaging for confirmation is required. Confirmatory imaging may be performed as early as 28 days later; alternatively, the scan performed at the next scheduled time point may be used as confirmation.
-  Tumor tissue for biomarker analysis from an archival tissue sample (not more than 42 days prior to signing consent) or newly obtained tumor tissue from a recent biopsy of a tumor lesion not previously radiated. Please see AFT 17 Correlative Science Manual for specimen collection instructions. If a NEW biopsy is performed, the investigator should ensure that adequate tissue is collected.

-  Patients who discontinue study treatment for a disease progression, will undergo a mandatory Safety Follow-up Visit approximately 30 days after the last dose of study treatment or before the initiation of a new antineoplastic treatment, whichever comes first. Patients with an AE of grade > 1 will be further followed until the resolution of the AE to Grade 0-1 or until beginning of a new antineoplastic therapy, whichever occurs first.

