#### **Measurement of Treatment/Intervention Effect**

##### **Target Lesions & Target Lymph Nodes**

- **Measurable lesions** up to a maximum of 5 lesions representative of all involved organs, should be identified as “Target Lesions” and recorded and measured at baseline. These lesions can be non-nodal or nodal where no more than 2 lesions are from the same organ and no more than 2 malignant nodal lesions are selected.

**Note:** If fewer than 5 target lesions and target lymph nodes are identified (as there often will be), there is no reason to perform additional studies beyond those specified in the protocol to discover new lesions.

- **Target lesions and target lymph nodes** should be selected on the basis of their size, be representative of all involved sites of disease, but in addition should be those that lend themselves to reproducible repeated measurements. It may be the case that, on occasion, the largest lesion (or malignant lymph node) does not lend itself to reproducible measurements in which circumstance the next largest lesion (or malignant lymph node) which can be measured reproducibly should be selected.
- **Baseline Sum of Dimensions (BSD):** A sum of the longest diameter for all target lesions plus the sum of the short axis of all the target lymph nodes will be calculated and reported as the baseline sum of dimensions (BSD). The BSD will be used as reference to further characterize any objective tumor response in the measurable dimension of the disease.

- **Post-Baseline Sum of the Dimensions (PBSD):** A sum of the longest diameter for all target lesions plus the sum of the short axis of all the target lymph nodes will be calculated and reported as the post-baseline sum of dimensions (PBSD). If the radiologist is able to provide an actual measure for the target lesion (or target lymph node), that should be recorded, even if it is below 0.5 cm. If the target lesion (or target lymph node) is believed to be present and is faintly seen but too small to measure, a default value of 0.5 cm should be assigned. If it is the opinion of the radiologist that the target lesion or target lymph node has likely disappeared, the measurement should be recorded as 0 cm.
- **The minimum sum of the dimensions (MSD)** is the minimum of the BSD and the PBSD.

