## 20. STATISTICAL ANALYSIS PLAN

The primary analysis will include all randomized patients but exclude ineligible patients or patients who cancel this study before receiving any protocol treatment.

The primary efficacy endpoint is PFS, which is defined as the time from the date of randomization to the date of earliest radiographic disease progression or death. If the subject does not experience radiographic disease progression or death, then the data will be censored at the date of the last disease assessment. PFS will be analyzed by Kaplan Meier methodology and compared between arm E and arm C, using a log-rank test stratified by disease type (sensitive vs refractory). A two-sided, stratified log-rank test P value will be provided. Median PFS time will be calculated and 95% confidence interval for median PFS will be presented. Overall survival (OS) will be analyzed in a similar manner as PFS.

Late treatment effect is often expected for immunotherapy. For this reason, a weighted log rank test with Harrington-Fleming weights that optimize the expected late treatment effect will be conducted as a supplementary analysis for both PFS and OS. In particular, the following three parameter settings will be used: (1)  $\rho = 0$  and  $\gamma = 0.5$ ; (2)  $\rho = 0$  and  $\gamma = 1$ ; and (3)  $\rho = 0$  and  $\gamma = 2$  (39).

The proportion of subjects with objective response as assessed by the investigator using RECIST version 1.1 will be evaluated for randomized subjects. The objective response rate will be estimated and compared between arm E and arm C, using a Cochran-Mantel-Haenszel (CMH) test stratified by tumor volume. A two-sided, stratified CMH test P value will be provided. In addition, a 95% confidence interval will be constructed for the estimated proportions. Similar analysis will be conducted for disease control rate (DCR), which is defined as the proportion of patients achieving complete, partial and stable disease after the protocol treatment.

All subjects who receive at least one dose of the study drug will be included in safety analysis. Treatment-related toxicity will be summarized by grade, type and system organ

class. Comparisons of the percentages of subjects experiencing an adverse event between arm E and arm C will be performed using Fisher's exact test.

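### The ORR and DCR tests are stratified by an undefined tumour volume rather than by disease type, the only randomisation factor

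*Combined protocol and SAP*

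**What the plan says.** Section 20 states that ORR will be compared between arms "using a Cochran-Mantel-Haenszel (CMH) test stratified by tumor volume", with a two-sided p-value. It then says "Similar analysis will be conducted for disease control rate (DCR"), so DCR inherits the same stratifier. In the same section the PFS comparison is made "using a log-rank test stratified by disease type (sensitive vs refractory"), and OS is to be analysed in a similar manner.

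Sections 8.4 and 19 name one randomisation factor, disease type. Section 5.1.2 explains why it matters for this endpoint: "topotecan leads to a differential response in SCLC patients with sensitive vs refractory disease, which we do not anticipate in those receiving pembrolizumab". Objective 6.2(iii) asks for ORR by disease type.

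Tumour size is measured. Baseline scans are required (Section 9.1, footnote 16: "The initial tumor imaging will be performed within 14 days prior to the first dose of study treatment"). Section 15.1.3 defines a baseline sum of dimensions (BSD) from lesion diameters and nodal short axes, and gives its purpose: "The BSD will be used as reference to further characterize any objective tumor response in the measurable dimension of the disease". No section turns that sum into strata or ties it to the CMH test.

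**The concern.** A CMH test needs categorical strata fixed in advance. Here the measure (a true volume, the BSD or something else), the number of levels and the cut-points are all open. Whoever runs the analysis must choose them after the plan was written. Treatment is known to all parties (Section 8.4), response is read by the investigator (Section 20), and the sponsor monitors unblinded aggregate efficacy data (Section 17.2.3).

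The test also leaves out the one factor that the randomisation balances and that the protocol itself ties to response. At stake are the pre-specification of a secondary comparison that has its own power statement in Section 19.1, and consistency between design and analysis.

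**Working it through.** **1. The plan's own ORR power.** Section 19.1 gives about 82% for 12% vs 32% with 31 control and 62 pembrolizumab patients at one-sided 0.10. Using the unstratified pooled-variance normal formula:

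- Pooled rate = (31 × 0.12 + 62 × 0.32)/93 = 0.2533.
- Null SE = √[0.2533 × 0.7467 × (1/31 + 1/62)] = 0.0957.
- Alternative SE = √[0.12 × 0.88/31 + 0.32 × 0.68/62] = 0.0832.
- Power = Φ[(0.20 − 1.2816 × 0.0957)/0.0832] = Φ(0.93) = 82.4%.

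The stated figure is reproduced. It involves no stratifier, so it neither supports nor depends on tumour volume.

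**2. How far disease type separates response.** Section 3.1 reports three single-arm topotecan studies, sensitive vs refractory: "37.8% among sensitive patients, 6.4% among refractory patients"; 14% vs 2%; and "19% (median survival, 26.6 weeks) and 3% (median survival, 20.4 weeks) for patients with sensitive and refractory disease, respectively". Those studies divide the groups at 90 days, whereas this trial uses 60, so the rates are a guide only.

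**3. Simulated CMH tests.** In each stratum *k*, let *a* be responders on pembrolizumab, *m* all responders, *n*E and *n*C the arm sizes and *t* the total. The statistic is

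Σ(*a* − *n*E·*m*/*t*) / √Σ[*n*E·*n*C·*m*(*t* − *m*)/(*t*²(*t* − 1))],

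without continuity correction, compared with 1.2816. Each setting used 8,000 trials of 93 patients, allocated 2:1 in blocks of three within disease type as a stand-in for dynamic allocation.

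Assumptions that are not document figures:

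- Pembrolizumab ORR is 32% in both strata, following Section 5.1.2.
- The sensitive share is set so that control ORR is 12%: share = (0.12 − refractory rate)/(sensitive rate − refractory rate).
- Size is cut at the 25th, 33rd, 50th, 67th or 75th percentile.
- Size is either unrelated to response or has an odds ratio of 0.5 per SD.

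| Control rates, sensitive / refractory | Sensitive share | Power, disease type | Power, unstratified | Five cut-points disagree, size unrelated | Same, odds ratio 0.5 per SD |
|---|---|---|---|---|---|
| 37.8% / 6.4% | 0.056/0.314 = 0.178 | 84.5% | 83.9% | 4.6% | 8.0% |
| 14% / 2% | 0.10/0.12 = 0.833 | 83.0% | 83.0% | 3.8% | 8.4% |
| 19% / 3% | 0.09/0.16 = 0.5625 | 84.1% | 84.0% | 4.2% | 8.8% |

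The Monte Carlo standard error for power is about 0.4 points.

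- **Size strata, size unrelated to response:** a single split has 82.6–83.8% power; three or four levels have 82.2–83.4%.
- **One size split against disease type:** the verdict differs in 1.4–2.5% of trials, or 3.5–4.8% at odds ratio 0.5.
- **Both arms at the control rates, nominal 10%:** disease type rejects in 9.6–11.0%, a single size split in 8.2–10.7%, and the most favourable of five splits in 9.8–11.9%.

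**4. Sensitivity to the assumed share.** With 19%/3% and the sensitive share fixed at 35%, 50% or 65%, control ORR is 8.6%, 11.0% or 13.4%. Power by disease type is 93.8%, 86.9% and 77.8%; unstratified it is 93.6%, 86.7% and 77.5%. The level moves with control ORR; the gap between tests stays at 0.2–0.3 points.

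**5. If pembrolizumab response also varies by disease type**, in the same proportion as control (20,000 trials; share 40–60%; control 3% refractory and 18–25.5% sensitive), power by disease type is 87–91% against 84–86% unstratified.

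**The case against.** The strongest reply is that this is a minor gap. Even picking the most favourable of five size cut-points raises the false-positive rate little: 9.8–11.9%, and 10.3–12.1% in a repeat of 4,000 trials per setting that included size related to response. That is at most about 2 points on a nominal 10% secondary test. This stands, and it limits the weight of the point. It does not supply the missing definition.

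Second, a CMH test may validly use a prognostic baseline covariate that was not a randomisation factor, and the null rates for a single size split are acceptable. If size is strongly prognostic (odds ratio 0.5 per SD), size splits gain about 0.2–1.1 points of power over disease type. This also stands: the statement that disease type loses no power holds against the unstratified test, not against every possible stratifier. But the documents give no reason to expect size to matter for response, whereas they give three sets of rates for disease type.

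Third, objective 6.2(iii) already requires ORR by disease type, so the difference will be reported. True, but that is description within strata, not the between-arm test. It also confirms which factor the authors thought relevant.

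Finally, the verdict figures use the one-sided 0.10 level of Section 19.1, while Section 20 promises a two-sided p-value and states no threshold. The disagreement rates are conditional on that level.

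**Conclusion.** The concern holds. As written, the ORR and DCR p-values cannot be computed, and the named stratifier departs without explanation from the only randomisation factor and from the PFS analysis in the same section.

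The size is modest. Results under different size cut-points would conflict in roughly 4–9% of trials, depending on how strongly size relates to response, and the false-positive risk rises by about 2 points at most. These figures rest on assumed sensitive shares, a flat 32% response on pembrolizumab and one assumed non-null odds ratio for size.

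Power is not the issue. PFS, OS and arm-level ORR with its 95% interval, which meets objective 6.2(i), are unaffected, and DCR is not a listed objective. The point should be fixed because a named secondary comparison ought to be fully specified and the remedy is nearly free.

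**What to change.** In Section 20, replace tumour volume with disease type (sensitive vs refractory) as used at randomisation, and state that it applies to both the ORR and the DCR tests.

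The qualifier matters. Section 7.1 also counts non-response to first-line chemotherapy as refractory, while Section 8.4 uses only the 60-day limit; Section 3.3.1 places the limit at more than 60 days where the other sections use 60 or more. Using the stratum entered at randomisation settles the data source for the test. The definitions themselves still need to be reconciled.

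If a size stratum was intended, define it from the BSD of Section 15.1.3, fix the cut-point before analysis, and report it as an additional analysis.

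The cost is a wording change under Section 21.5, either as a formal amendment with IRB approval or as an administrative clarification notified to the IRB. No new data are needed: disease type is required to randomise and is listed for collection in Section 9.1, footnote 6.

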Study Design	This is a multi-institutional, randomized, open-label phase II study of pembrolizumab compared to topotecan, administered to patients with SCLC who have progressed or relapsed after first-line treatment with etoposide and platinum. Patients will be randomized in a 2:1 fashion to receive pembrolizumab or topotecan. Participants in the topotecan arm that progress will be allowed to cross-over to the pembrolizumab arm.
Study Treatment Plan	Pembrolizumab Arm: Pembrolizumab will be administered via IV infusion at 200 mg every 3 weeks, and treatment continued for up to 24 months, until documented disease progression, unacceptable side effects or intercurrent illness that prevents further administration of treatment, investigators' decision to

	
withdraw the subject, subject withdraws consent, pregnancy of the patient, noncompliance of the patient, or for administrative reasons.
 
Topotecan Arm: Topotecan will be administered via IV infusion at 1.25 mg/m^2 on days 1 to 5 of a 3-week cycle. Pegfilgrastim may be given on day 6, 7, or 8 to offset neutropenia. Patients who progress in the topotecan arm will be allowed to cross-over to the pembrolizumab arm.

Efficacy Assessments	
Patients will be evaluated every 6 weeks (42 ± 7 days) with radiographic imaging to assess response to treatment. Investigators will make all treatment-based decisions using RECIST 1.1.

Safety Assessments	
Patients will be evaluated clinically by physical exam and with routine blood work every 21 days. Adverse events will be monitored throughout the Study and graded in severity according to the guidelines outlined in the NCI Common Terminology Criteria for Adverse Events (CTCAE) version 4.

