-  Patients who discontinue study treatment for a reason other than disease progression will move into the Follow-up Phase and should be assessed every 6 weeks ( $42 \pm 7$  days) by radiologic imaging to monitor disease status, development of drug related SAEs and ECIs/irAEs, and initiation of a new antineoplastic therapy. Follow-up visit 1 should be scheduled 6 weeks after the last dose of study treatment. Unless otherwise noted in the flow chart, every effort should be made to collect patient information until the start of new antineoplastic therapy, disease progression, or death, whichever comes first.
-  Once a patient experiences disease progression or starts a new antineoplastic therapy, the patient moves into the Survival Follow-up Phase and should be contacted by telephone every 3 months to assess for survival status, development of drug related SAEs and ECIs/irAEs and the start of new antineoplastic therapy if applicable.
-  Record all AEs occurring within 30 days after the last dose of study treatment or until initiation of a new antineoplastic therapy, whichever comes first. Report all SAEs (related and unrelated to study treatment) occurring within 90 days of the last dose of study treatment or the start of new anti-cancer treatment, whichever comes first. All ECIs/irAEs occurring within 90 days of the last dose of study treatment should be reported regardless of initiating new anticancer therapy. After this time, report only SAEs and ECIs/irAEs that are considered related to study treatment.
-  If archival sample is not available, fresh tissue samples will be collected for correlative studies.
-  Those patients receiving pembrolizumab will undergo a biopsy obtained during week 4 to 6 of treatment for biomarker analysis, if clinically feasible and safe. A tumor lesion not previously radiated (required for PD-L1 determination) should be biopsied. The tumor sample must be sent to the AFT-Biorepository. See AFT 1 Correlative Science Manual for additional details.
-  Patients on the topotecan arm who progress and are to cross-over to the pembrolizumab arm, will undergo a biopsy just before initiating experimental treatment, if clinically feasible and safe. A tumor lesion not previously radiated (required for PD-L1 determination) should be biopsied. The tumor sample must be sent to the AFT-Biorepository.

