-  Whole blood samples for genomic analyses, and peripheral blood cell/serum plasma samples for correlatives will be collected for all patients at screening, at week 4-6 biopsy, at imaging during all cycles, and at progression/cross-over. Samples will be collected per Section 12. Note that each time point requires differing types of blood collection. Please refer to the lab manual for detailed instructions on sample collection. § For patients who cross-over from the topotecan arm to the pembrolizumab arm, they will undergo the same assessments and procedures from study start, except that a repeat tumor biopsy will not be performed during weeks 4 to 6.

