### **17. ADVERSE EVENTS**

An adverse event (AE) is defined as any untoward medical occurrence in a patient or clinical investigation subject administered a pharmaceutical product and which does not necessarily have to have a causal relationship with this treatment. An adverse event can therefore be any unfavorable and unintended sign (including an abnormal laboratory finding, for example), symptom, or disease temporally associated with the use of a medicinal product or protocol-specified procedure, whether or not considered related to the medicinal product or protocol-specified procedure. Any worsening (i.e., any clinically significant adverse change in frequency and/or intensity) of a preexisting condition that is temporally associated with the use of pembrolizumab is also an adverse event.

Changes resulting from normal growth and development that do not vary significantly in frequency or severity from expected levels are not to be considered adverse events. Examples of this may include, but are not limited to onset of menses or menopause occurring at a physiologically appropriate time.

Adverse events may occur during the course of the use of pembrolizumab (or topotecan) during this study, or as prescribed in clinical practice, from overdose (whether accidental or intentional), from abuse and from withdrawal.

Progression of small cell lung cancer is not considered an adverse event unless it is considered to be drug related by the investigator.

The prompt reporting of adverse events is the responsibility of each investigator engaged in clinical research, as required by Federal Regulations. Adverse events must be described and graded using the terminology and grading categories defined in the NCI's Common Terminology Criteria for Adverse Events (CTCAE), Version 4.0. The CTCAE is available at [ctep.cancer.gov/protocolDevelopment/electronic\\_applications/ctc.htm](http://ctep.cancer.gov/protocolDevelopment/electronic_applications/ctc.htm). Attribution to protocol treatment for each adverse event must be determined by the investigator and reported on the required forms, using the codes provided.

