## 17.1. ROUTINE ADVERSE EVENT REPORTING

Adverse event data collection and reporting, which are required as part of every clinical study are done to ensure the safety of patients enrolled in the studies as well as those who will enroll in future studies using similar agents. AEs will be recorded as part of medical history during Screening. All adverse events that occur after the consent form is signed but before treatment allocation/randomization must be reported by the investigator if they cause the subject to be excluded from the study, or are the result of a protocol specified intervention, including but not limited to washout or discontinuation of usual therapy, diet, placebo treatment or a procedure. Any new AEs or increase of a documented AE from screening/history will be recorded from the time of the first treatment allocation/randomization through 30 days following cessation of treatment. Adverse events are reported in a routine manner at scheduled times according to the study calendar in Section 9. All adverse events are entered into the eCRF in Rave. The investigator will make every attempt to follow all subjects with non-serious adverse events for outcome.

Adverse events will not be collected for patients during the pre-screening period as long as that patient has not undergone any protocol-specified procedure or intervention. If the patient requires a blood draw, fresh tumor biopsy etc., the patient is first required to provide consent to the main study and AEs will be captured according to guidelines for standard AE reporting.

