### **17.3. EVALUATING ADVERSE EVENTS**

An investigator who is a qualified physician will evaluate all adverse events according to the NCI Common Terminology for Adverse Events (CTCAE), version 4.0. Any adverse event which changes CTCAE grade over the course of a given episode will have each change of grade recorded on the adverse event case report forms/worksheets.

All adverse events regardless of CTCAE grade must also be evaluated for seriousness. See Table 13 below for additional guidance.

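### The between-arm adverse event comparison sets no cut-off at cross-over, so events on cross-over pembrolizumab would count against topotecan; Table 13's pembrolizumab-only relatedness question also needs reconciling

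*Combined protocol and SAP*

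**What the plan says.** **Analysis.** Section 20 puts everyone with at least one dose in the safety analysis and then says: "Comparisons of the percentages of subjects experiencing an adverse event between arm E and arm C will be performed using" Fisher's exact test. It gives no observation window, no cut-off and no separate summary for the cross-over phase. Section 19 defines arms E and C by the 2:1 randomisation, and Section 19.1 gives 62 and 31 patients.

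**Cross-over.** The Study Treatment Plan in Section 1.1 says: "Patients who progress in the topotecan arm will be allowed to cross-over to the pembrolizumab arm". Section 10.1 repeats the allowance. The cross-over footnote to Table 2 says: "For patients who cross-over from the topotecan arm to the pembrolizumab arm, they will undergo the same assessments and procedures from study start", with an exception for one biopsy.

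**Collection.** Under Section 17.1, new or worsening events "will be recorded from the time of the first treatment allocation/randomization through 30 days following cessation of treatment". Footnote 22 to Table 2 reads "Record all AEs occurring within 30 days after the last dose of study treatment or until initiation of a new antineoplastic therapy", whichever is earlier. Footnote 19 sets a "mandatory Safety Follow-up Visit approximately 30 days after the last dose of study treatment or before the initiation of a new antineoplastic treatment". Neither footnote says whether cross-over pembrolizumab is such a new treatment.

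**Relatedness.** Section 17 says: "Attribution to protocol treatment for each adverse event must be determined by the investigator and reported on the required forms, using the codes provided". Section 5.1.2 promises treatment-related toxicity for both drugs by arm. Section 19.3 counts events in either arm that are probably, possibly or definitely related to study treatment. Section 17.3 adds "See Table 13 below for additional guidance". That table asks only whether pembrolizumab caused the event, takes Yes or No, and lists not having received pembrolizumab under No.

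**The concern.** Safety is a secondary objective (Section 6.2), and this is its only planned between-arm test. If a patient randomised to topotecan progresses, crosses over and then has an immune-type event, the safety table needs a rule for that event. Without one, the arm C percentage is built from two drugs given in sequence, while the arm E percentage comes from one. The distortion depends on the type of event:

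- Events typical of pembrolizumab appear in both arms, so the difference shrinks.
- Events typical of topotecan barely move.
- Events equally common on both drugs rise in arm C, because those patients have two chances to have them.

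The trial is open-label, so the rule should be fixed before anyone looks at the tables. Dates of dosing and onset would allow the periods to be separated; only the rule is missing.

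Table 13 is a separate matter of data capture. Its relatedness question does not match Sections 5.1.2, 17 and 19.3 in the drug asked about, and its Yes/No answer does not match the scale in Section 19.3. It has no bearing on the all-event Fisher test.

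**Working it through.** **The plan's own figures.** Section 20 gives no figure for the adverse event comparison, so there is none to reproduce. The main design figure is not in dispute and does reproduce. With 86 events, hazard ratio 0.60, 2:1 allocation and one-sided 0.10, √(86 × 2/3 × 1/3) × |ln 0.60| − 1.2816 = 0.95, which gives 82.9% power. The stated 59/27 event split gives 82.0%, against the plan's approximate 82%.

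**Inputs.**
- From Section 19.1: 62 patients in arm E and 31 in arm C.
- Assumed, because the documents give none of them: event rates pE and pC on each drug, cross-over share c of 40% or 60%, and a two-sided 0.05 level.

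**Formula.** If cross-over events count in arm C, its rate becomes pC′ = pC + (1 − pC) × c × pE. This assumes that crossing over is unrelated to earlier events and that cross-over patients carry the full pembrolizumab risk. Power is exact: the Fisher test is evaluated for every pair of counts and weighted by the two binomial distributions.

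**Worked cases at 40% cross-over.**
- Pembrolizumab-typical, 20% vs 2%: 0.02 + 0.98 × 0.4 × 0.20 = 0.098.
- Topotecan-typical, 5% vs 40%: 0.40 + 0.60 × 0.4 × 0.05 = 0.412.
- Equal, 40% on both: 0.40 + 0.60 × 0.4 × 0.40 = 0.496.

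**Results.** Chance of a significant difference:

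| pE vs pC | With cut | No cut, c = 40% | No cut, c = 60% |
|---|---|---|---|
| 10% vs 2% | 15% | 5% | 3% |
| 20% vs 2% | 69% | 17% | 8% |
| 20% vs 2%, half risk after cross-over | 69% | 36% | 25% |
| 30% vs 2% | 96% | 38% | 16% |
| 5% vs 40% | 98% | 99% | 99% |
| 20% vs 20% | 4% | 9% | 15% |
| 40% vs 40% | 4% | 13% | 25% |

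In the last two rows the counted arm C rate is 26% or 30%, and 50% or 54%. The excess comes from the counting rule and not from topotecan.

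**The case against.** Five objections deserve an answer.

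1. **The ambiguity is narrower than it could be made to sound.** A reader might infer that cross-over patients could equally be counted in arm E. The documents do not support that: Sections 19 and 19.1 define the arms by randomisation, and the only support is the loose reference in Section 1.1 to crossing over to the pembrolizumab arm. Nor is it likely that collection stops at cross-over. Cross-over pembrolizumab is protocol treatment under Section 10.1, and the assessments restart. The synopsis does call it a new treatment in the biopsy text, so a clarification is fair but minor. This objection stands, and it leaves one live reading: count the events in arm C.

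2. **The magnitudes are assumed.** This stands. They show sensitivity to the missing rule and do not predict this trial's results. Power is also an imperfect yardstick for a safety summary that has no hypothesis.

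3. **The cut has its own bias.** Arm C would lose part of its 30-day tail while arm E keeps its own, and the planned median PFS differs (12 vs 20 weeks), so observation is unequal even with a cut. This stands and is the reason for showing time at risk.

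4. **Table 13 may do no harm.** A reader might infer that topotecan-related events would be lost, or that the Section 19.3 rule could never trigger in arm C. That would require every site to follow Table 13 and disregard Section 17. Section 17 makes attribution to protocol treatment mandatory, Section 17.2 requires attribution of every death, and Table 12 requires serious events to be reported whether or not related. The forms are not in the documents. What stands is an inconsistency in the text.

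5. **Table 13 is not an analysis choice and should not add weight to the main point.** Agreed; it is kept as secondary.

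**Conclusion.** The concern holds. As written by randomised arm, the Section 20 comparison would count events on cross-over pembrolizumab in arm C, because nothing limits the period and those events are collected. The direction of the distortion follows from the design. Its size depends on the assumed rates and cross-over shares: in the 20% vs 2% case power falls from 69% to between 8% and 36%, and in the 40% vs 40% case a chance of about 4% becomes 13% to 25%. Comparisons of topotecan-typical events hardly change.

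Table 13 conflicts with Sections 5.1.2, 17 and 19.3. This is a point to reconcile and not evidence of missing data. Neither point touches the primary PFS analysis. The sponsor should make the change, but it is not critical to the trial's main conclusion.

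**What to change.** **Section 20.**
- Base the between-arm comparison on the randomised-treatment period, counting arm C events up to the first cross-over dose of pembrolizumab.
- Report cross-over-phase events in a separate column.
- Show time at risk beside the percentages.
- List events that the investigator attributes to topotecan and that start after that dose but within 30 days of the last topotecan dose.

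**Table 2, footnotes 19 and 22.** State whether cross-over pembrolizumab is a new antineoplastic treatment, worded so that cross-over-phase events are still collected.

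**Table 13 (secondary).** Reconcile it with Sections 5.1.2, 17 and 19.3, so that relatedness to the study drug received is recorded on the scale that Section 19.3 uses.

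**Cost.** A few sentences in the plan, one date flag in programming, one extra safety column, one listing, and a small edit to Table 13 and possibly to the form. The statistical price is the shortened arm C tail described above; the time-at-risk display and the listing make it visible but do not remove it.
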